2 STUDY OBJECTIVES

2.1 Primary Objective(s)

The primary objectives of this study are to:

- Determine the safety and tolerability of the proposed Debio 1562 dose regimens in combination with rituximab;
- Determine the anti-tumor activity of the proposed Debio 1562 dose regimens in combination with rituximab.

2.2 Secondary Objectives

The secondary objectives of this study are to:

- Characterize the pharmacokinetics (PK) of Debio 1562 in combination with rituximab;
- Determine time to event outcomes (progression-free survival [PFS], time to response [TTR], duration of response [DoR], and overall survival [OS]);
- Assess the immunogenicity of Debio 1562 (anti-drug antibodies [ADA]) when administered in combination with rituximab.

2.3 Exploratory Objectives

The exploratory objectives of this study are to:

- Correlate the extent of CD37 and CD20 antigen expression in tumor samples with anti-tumor activity of Debio 1562 and rituximab combination;
- [REDACTED]
- Assess health-related quality of life (HRQoL).

3 STUDY ENDPOINTS

3.1 Primary Endpoint(s)

The primary endpoints of this study are:

- Incidence of treatment-emergent adverse events (TEAEs), clinically significant changes in clinical laboratory test results, electrocardiogram (ECG), and vital sign measurements;
- Objective response rate (ORR) defined as the proportion of subjects with a best overall response of partial response (PR) or complete response (CR) as assessed by the 2014 Lugano classification of response assessments of NHL (Cheson, 2014).

3.2 Secondary Endpoints

The secondary endpoints of this study are:

- PK parameters for both Debio 1562 and rituximab (evaluated but not limited to): maximum concentration (C_{max}), area under the curve (AUC_{0-t} , AUC_{inf}), terminal half-life ($t_{1/2}$), clearance, volume of distribution at steady state (V_{ss}), and time to reach maximum concentration (T_{max});
- Efficacy time-to-event endpoints:
 - o Progression-free survival (PFS) defined as the duration between the first dose date of Debio 1562 and the date of progressive disease (PD) or death due to any cause, whichever occurs first. As this study has randomized and non-randomized parts, starting date for the calculation of PFS is set to the first dose date of Debio 1562;
 - o Time to response defined as the duration between the first dose date of Debio 1562 and the date of first objective response (PR or CR). This will be computed for responders only. As this study has randomized and non-randomized parts, starting date for the calculation of TTR is set to the first dose date of Debio 1562;
 - o Duration of response (DoR) defined as the duration between the date of first objective response (PR or CR) and the date of PD or death due to any cause, whichever occurs first. This will be computed for responders only;
 - o Overall survival (OS) defined as the duration between the first dose date of Debio 1562 and the date of death due to any cause. As this study has randomized and non-randomized parts, starting date for the calculation of OS is set to the first dose date of Debio 1562;
- Immunogenicity of Debio 1562: Presence of human anti-drug antibody.

Unless otherwise specified in subsequent sections, pharmacokinetics, [REDACTED] and immunogenicity analyses are beyond the scope of this document. They will be covered by dedicated analysis plans.

3.3 Exploratory Endpoints

The exploratory endpoints of this study are:

- Expression levels of CD37, CD20 by immunohistochemistry (IHC, protein) and/or mRNA detection and correlation of these measures to clinical response criteria;
 - [REDACTED]
 - [REDACTED]
 - [REDACTED]
 - [REDACTED]
 - [REDACTED]
 - [REDACTED]
 - [REDACTED]
- Health-related quality of life (HRQoL) will be evaluated based on the functional assessment of cancer therapy-lymphoma (FACT-Lym). It is comprised of:
 - o The functional assessment of cancer therapy-general (FACT-G) version 4 (27 items), scored in four domains:
 - Physical well-being (7 items);
 - Social/Family well-being (7 items);
 - Emotional well-being (6 items);
 - Functional well-being (7 items);
 - o The FACT-Lymphoma Subscale, LymS, reflecting Lymphoma specific concerns (15 items).

The exploratory analyses including HRQoL analyses are beyond the scope of this document. They will be covered by dedicated analysis plans.

[REDACTED]

[REDACTED]

[REDACTED]

4 STUDY DESIGN AND TREATMENT

4.1 Study Design

This is an open label, multicenter, adaptive phase 2 clinical trial of Debio 1562 in combination with rituximab in subjects with DLBCL and other subtypes of B-cell NHL.

The clinical trial includes a screening period, a treatment period, an end of treatment visit, a 30-day safety follow-up visit, a response follow-up period if relevant, and a survival follow-up period if relevant.

The clinical trial consists of three parts: a safety run-in with its expansion Phase 2¹ (part 1), initial assessment of safety and efficacy of Q3W and QW dosing regimens of Debio 1562 (part 2) and an expansion (part 3).

4.1.1 Part 1: Safety run-in and Phase 2

¹ Phase 2 is described in protocol versions 1, 2, and 3, and includes Cohort 1 (R/R DLBCL) and Cohort 2 (other NHL)

Subjects with DLBCL, follicular lymphoma (FL), mantle cell lymphoma (MCL), marginal zone lymphoma/mucosa associated lymphoid tissue (MZL/MALT) or other NHL subtypes (with Sponsor's approval) are eligible for enrollment in the safety run-in part.

During the safety run-in, subjects are given Debio 1562 and rituximab IV on day 1 of each 21 days cycle. Debio 1562 is given at a dose of 0.7 mg/kg, followed by 375 mg/m² of rituximab.

Safety run-in continued with a Phase 2: Cohort 1 (R/R DLBCL) and Cohort 2 (other R/R NHL subtypes; see protocol versions 1, 2, and 3).

The Safety Review Committee (SRC) is comprised of the Sponsor's Medical Director and Investigators from participating sites, and is responsible for safety data review during the course of the trial.

Treatment emergent adverse events (TEAEs) occurring in patients enrolled into the safety run-in phase will be reviewed by the SRC. Once the Phase 2 dose is determined by the SRC, Cohorts 1 and 2 will open and enroll simultaneously, with rituximab and Debio 1562 being administered at the same schedule used in the safety run-in phase.

4.1.2 Part 2: Initial assessment of safety and efficacy of Q3W and QW dosing regimens of Debio 1562

Subjects with pathologically and clinically confirmed diagnosis of relapsed DLBCL are eligible for enrollment into two parallel cohorts.

In cohort A, subjects are given Debio 1562 IV and rituximab IV on day 1 of each 21 days cycle. Debio 1562 is given at a dose of 0.7 mg/kg, followed by 375 mg/m² of rituximab (same dose and schedule as in part 1).

In cohort B, subjects are given Debio 1562 IV once every week (QW) and rituximab IV Q3W. Debio 1562 is given at a dose of 0.4, 0.2 and 0.2 mg/kg on day 1, 8 and 15 of each 21 days cycle. Rituximab is given at a dose of 375 mg/m² on day 1 of each 21 days cycle.

Subjects in both cohorts will be treated for a maximum of six 21-day cycles. Subjects may exceptionally be granted treatment extension.

An independent data monitoring committee (IDMC), comprised of independent experts in the field of hematology, oncology, PK and biostatistics, will perform regular reviews of cumulative safety, efficacy, and PK data in both cohorts A and B.

Assignment of subjects to cohort A and cohort B will be done through a central allocation system (IWRS). One-to-one randomization will be done when both cohorts are open for recruitment and automatic allocation of subjects to cohort A during IDMC review of cohort B.

4.1.3 Part 3: Expansion

Part 3 of the study will enroll additional subjects with pathologically and clinically confirmed diagnosis of relapsed DLBCL to further assess the safety, proof of activity and PK of the dosing schedule recommended following the evaluation of Part 2 by the IDMC.

IDMC will perform regular reviews of cumulative safety, proof of activity and PK data available.

Patients of the planned Part 3 were recruited under Part 2/3, no specific distinction was made between cohort 2 and 3.

4.2 Safety Review Committee and Independent Data Monitoring Committee

4.2.1 Safety Review Committee

The safety review committee (SRC), comprised of the Sponsor's medical director and investigators from participating sites, is responsible for safety data review during the course of part 1 (safety run-in). Please refer to Section 4.1.3.1 of the protocol for additional information on the SRC. The SRC determines whether the Debio 1562 dose of 0.7 mg/kg should be evaluated in the next part of the study, or whether an alternative dose should be evaluated.

4.2.2 Independent Data Monitoring Committee

The IDMC, comprised of independent experts in the field of hematology, oncology PK and biostatistics, will be responsible for the review of safety, proof of activity and PK data during the course of part 2 and part 3 of the clinical trial.

Available cumulative safety, PK and anti-tumor activity data will be provided for review by the IDMC:

- **For part 2, cohort A:**
 1. Once the 10th subject is evaluable for efficacy (i.e., patients should have performed at least one post baseline objective response assessment - unless there is earlier clear evidence of PD). Enrollment in this cohort will continue during the IDMC review;
 2. Once the 15th subject is evaluable for efficacy (i.e., patients should have performed at least one post baseline objective response assessment - unless there is earlier clear evidence of PD). Enrollment in this cohort will continue during the IDMC review;
- **For part 2, cohort B:**
 1. Once the 3rd subject has completed one cycle of treatment. Enrollment in this cohort will continue during the IDMC safety review;
 2. Once the 6th subject has completed two cycles of treatment. Enrollment in this cohort will be paused during the IDMC safety review;
 3. Once the 12th subject has completed two cycles of treatment. Enrollment in this cohort will be paused during the IDMC safety review;

At IDMC review 2 or 3, PK evaluation might be available to support potential IDMC recommendation to explore new QW dosing schedule. At the maximum, only one potential new dosing will be explored. In such a case, the same IDMC reviews (1-3) as described above will be repeated for evaluation of this new schedule.

- **For part 3:**

After every 10 subjects have completed two cycles of treatment and are evaluable for efficacy (i.e., patients should have performed at least one post baseline objective response assessment - unless there is earlier clear evidence of PD).

Please refer to Section 4.1.3.2 of the protocol and to the IDMC charter for additional information on the IDMC.

4.3 Study Treatments

The investigational study drug, Debio 1562, will be provided by Debiopharm International S.A. in 20 mL glass vials each containing 5 mL of a protein concentration of 8.0 mg/mL Debio 1562 in aqueous buffered solution of pH 5.0 ± 0.3.

Rituximab will be supplied as a commercially available formulation.

4.4 Overall End-of-Study

The Overall End-of-Study is defined as the latter of the completion of the safety follow-up visit for the last patient remaining on treatment or one year from the last accrued patient's first visit.

4.5 Study Procedures

Please refer to [Appendix A](#), [Appendix B](#) and [Appendix C](#) for the description of the schedule of events. Study procedures are listed in Section 8 of the protocol.

5 RANDOMIZATION AND BLINDING

This is an open label clinical trial. [Table 1](#) is providing a description of the randomization characteristics and constraints during each study part.

Table 1 - Study Parts and Randomization

Study Part	Randomization	Comments
Part 1	No	Subjects are given Debio 1562 (0.7 mg/kg) and rituximab IV (375 mg/m ²) on day 1 of each 21 days cycle.
Part 2	Yes	One-to-one block randomization will be done when both cohort A and cohort B are open for recruitment. Please refer to Section 4.1 for the automatic allocation to the open cohort during IDMC review
Part 3	Yes	Open for enrolment if and only if at least one cohort is eligible for part 3: - One-to-one block randomization if both cohort A and cohort B are eligible to part 3; - If cohort A (resp. cohort B) is not eligible for part 3, subjects will be assigned to cohort B (resp. cohort A).

[REDACTED]

7 ANALYSIS POPULATIONS

7.1 Screened Population

All subjects screened will be part of the screened population.

7.2 All treated / Safety Population

The All treated/safety population will include all patients from the screened population who received at least one dose of Debio 1562. Reporting in the All treated population will be done per the actual cohort as defined in the protocol.

7.3 Efficacy Evaluable Population

All subjects who received at least one dose of Debio 1562 and rituximab, and had both baseline and post-baseline evaluable disease assessment (including clinical progressive disease) will be part of the efficacy evaluable population. Reporting in the efficacy evaluable population will be done per the assigned treatment and cohort as per protocol (version 7, Section 10.2).

7.4 Per protocol population

The per-protocol (PP) population will include all patients from the Efficacy evaluable population who do not have any protocol deviation that could confound the interpretation of efficacy analyses. Patients who died from disease progression before end of first cycle will also be part of the per-protocol population.

The protocol deviations that could confound the interpretation of efficacy analyses include violation of key eligibility criteria (inclusion and/or exclusion) designed to ensure a specific subject population. It also includes the failing to collect data necessary to interpret the primary efficacy endpoints.

A detailed description of the protocol deviations which will exclude patients from the PP population is given in [Appendix K](#).

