All patients will be contacted every 12 weeks ( $\pm$  4 weeks) from the time of the 30-day safety follow-up visit until one year from last patient's first study treatment.

**Statistical methods:** All statistical analyses will be performed using the most recently released and available Statistical Analysis Software (SAS) statistical software, unless otherwise noted. For categorical variables, the number and percent of each category within a parameter will be calculated. For continuous variables, the sample size (n), mean, median, and standard deviation, as well as the minimum and maximum values, will be presented. Missing data will not be imputed unless otherwise stated. There will be a summary of patient disposition, patient demographics, and baseline characteristics. PK parameters will be computed and presented in tables and listings. Plasma concentrations will be presented in graphs for each patient and by cohorts. Latest version of SAS or WinNonlin will be used for the PK analyses.

No formal interim analysis for efficacy will be performed; however, futility analyses will be conducted after 10 patients and, if deemed necessary, 15 patients in cohort A are evaluable for efficacy (i.e., patients should have performed at least one post baseline objective response assessment- *unless there is earlier clear evidence of PD*), as well as cumulative after enrollment of every 10 evaluable patients for efficacy (if deemed necessary) in study Part 3. At each analysis, futility will be evaluated using a Bayesian approach with a non-informative conjugate prior. The decision rule will be to recommend stopping for futility if there is sufficiently low probability (20% or less) that Objective Response Rate (ORR) exceeds the pre-specified (historical) control response of 40%. The primary analysis will be conducted after all enrolled patients reached their 3rd on-treatment scheduled response assessment or have discontinued from treatment. The final analysis will be triggered one year after the last accrued patient's first dose date. In the exceptional

case that after the final analysis a patient(s) might continue to receive study treatment under the protocol, any subsequent data generated from this patient(s) will be summarized in an addendum report to be issued after the last treatment of the last patient.

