##### **For cohort A (Part 2):**

- Once 10 patients are evaluable for efficacy (i.e., patients should have performed at least one post baseline objective response assessment- *unless there is earlier clear evidence of PD*). Enrollment in this cohort will continue during the IDMC review.
- Once 15 patients are evaluable for efficacy (i.e., patients should have performed at least one post baseline objective response assessment- *unless there is earlier clear evidence of PD*). Enrollment in this cohort will continue during the IDMC review.

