## 10.2. Analysis Populations

The following analysis populations will be considered:

- **Screened Population:**

All subjects screened will be part of the screened population.

- **Safety Population:**

All subjects who receive at least one dose Debio 1562 will be part of the safety population. Reporting in the safety population will be done against the actual treatment received.

- **Efficacy Evaluable Population:**

All subjects who received at least one dose of Debio 1562 and rituximab, and had both baseline and post-baseline evaluable disease will be part of the efficacy evaluable population. Reporting in the efficacy evaluable population will be done against the assigned treatment.

- **PK Population:**

All subjects who receive one dose of study drug and have at least one PK concentration result available (Debio 1562 or rituximab concentration, including value below limit of quantification). Reporting in the PK population will be done against the actual treatment received.

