## **10.5. Anti-Tumor Activity**

ORR – The best overall response will be determined by the Investigator for each evaluable patient as CR, PR, stable disease (SD), or relapsed disease/PD. The ORR will be tabulated by dose cohort assigned as well as the dose at which the response occurred along with the 80% and the 95% confidence interval (CI). To meet the definition of response-evaluable, patients must have undergone radiographic assessment at baseline, received at least one dose of Debio 1562 and rituximab, and must have had at least one post-dose tumor assessment.

OS – Overall survival will be analyzed using the Kaplan-Meier method. Median OS and 95% CI (if feasible) will be presented. The OS rate at one year along with the 95% CI will be estimated and presented.

DoR – The DoR will be estimated for all evaluable patients who achieve an objective response (PR or CR). Median duration and associated 95% CIs will be presented.

PFS – PFS will be analyzed using the Kaplan-Meier method. Median PFS and 95% CI (if feasible) and the rate of PFS at six months and at 1 year and their 95% CI will be estimated and presented.

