## **10.6. Analysis and Stopping Rules**

### **10.6.1. Futility Analyses**

No formal interim analysis for efficacy will be performed; however, futility analyses will be conducted after 10 patients and, if deemed necessary, 15 patients in cohort A are evaluable for efficacy (i.e., patients should have performed at least one post baseline objective response assessment- *unless there is earlier clear evidence of PD*), as well as cumulative after enrollment of every 10 evaluable patients for efficacy (if deemed necessary) in study Part 3. At each analysis, futility will be evaluated using a Bayesian approach with a non-informative conjugate prior.

[REDACTED]

[REDACTED]

[REDACTED]

[REDACTED]

[REDACTED]

[REDACTED]

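### A lymphoma death before the first scan with no clinical progression recorded falls outside the SAP's efficacy evaluable set, is added to the per-protocol set only in cycle 1, and so can drop out of ORR

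*SAP*

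**What the plan says.** Four definitions bear on whether a patient who fails before the first scan is evaluable for response.

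- **Futility review** (Protocol 4.1.3.2 and 10.6.1; SAP 4.2.2): "patients should have performed at least one post baseline objective response assessment - unless there is earlier clear evidence of PD". A clear early progressor counts. Death is not named.
- **Protocol 10.2 and 10.5**: under 10.2 the patient must have received both drugs and "had both baseline and post-baseline evaluable disease will be part of the efficacy evaluable population". Section 10.5, on ORR, begins "To meet the definition of response-evaluable, patients must have undergone radiographic assessment at baseline" and goes on to require at least one tumor assessment after dosing. Neither section makes an exception for early progression or death.
- **SAP 7.3**: the patient must have received both drugs and "had both baseline and post-baseline evaluable disease assessment (including clinical progressive disease) will be part of the efficacy evaluable population". Death is not mentioned.
- **SAP 7.4**: the per-protocol set is drawn from the efficacy evaluable set, less patients with confounding deviations. It then adds: "Patients who died from disease progression before end of first cycle will also be part of the per-protocol population".

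SAP 10.2 runs the response summaries on the efficacy evaluable set and adds the All treated set for OS and PFS only. SAP 10.2.3 tests ORR by cohort against 40%. SAP 11 refers to the protocol's amendment history and lists no departure from the protocol's population definitions.

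**The concern.** Whether an early lymphoma death counts in the ORR denominator depends on two things unrelated to the drug's activity: whether someone recorded clinical progression before the patient died, and which document is followed. A patient who dies of lymphoma without responding is a treatment failure. Leaving that patient out removes a non-responder from the denominator and nobody from the numerator, so ORR can only go up. In an open-label study with investigator-assessed response, this rule should be settled before database lock.

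The add-on in SAP 7.4 also sits oddly. It recognises that a cycle 1 death from progression is informative, but secures that patient's place only in the stricter set. The set on which ORR is tested may not contain the patient. The SAP deals with the same situation for PFS: in SAP 10.2.4.1, the fifth censoring rule counts a death within 190 days as an event even with no post-baseline assessment. Response has no matching rule.

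**Working it through.** **Timing.** A cycle is 21 days (SAP 9.1), so cycle 1 ends at about day 21. The first scan is due at 6 weeks ± 1 week (SAP 10.2.2), which is 42 ± 7, or day 35 to 49.

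**Who is in which set.** Take a patient who received both drugs, had a baseline scan, has no excluding deviation, and failed before any post-baseline scan.

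| Patient | Futility | Protocol 10.5 (literal) | SAP 7.3 | SAP 7.4 |
|---|---|---|---|---|
| Clinical PD recorded | In | Out | In | In |
| Lymphoma death by end of cycle 1, no PD recorded | Only if taken as clear evidence of PD | Out | Out | In |
| Lymphoma death from day 22 to first scan, no PD recorded | Only if taken as clear evidence of PD | Out | Out | Out |

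The second row is the failure of nesting: in the per-protocol set, not in its parent. The third row is the gap. The first row is where Protocol 10.5 departs from both the futility definition and SAP 7.3.

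**Size.** The plan has no visible figure to reproduce, since the sample size text is blacked out. Assumptions: N = 30 treated patients (the protocol's approximate Part 3 number, used only as an illustration), true ORR 40% among all treated, and a one-sided exact test of 40% at 5%. No test level is visible.

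If a share *e* of treated patients are early failures and are dropped, the response probability among those left is 0.40 / (1 − *e*). The number dropped is binomial(30, *e*). The rejection rate is the exact test's rejection probability at each remaining sample size, averaged over that number.

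| Share dropped | Expected ORR | Rejection rate |
|---|---|---|
| 0 | 40.0% | 4.8% |
| 2% | 0.40/0.98 = 40.8% | 5.2% |
| 3.3% (1 in 30) | 0.40/0.967 = 41.4% | 5.7% |
| 5% | 0.40/0.95 = 42.1% | 6.5% |
| 10% | 0.40/0.90 = 44.4% | 9.1% |
| 15% | 0.40/0.85 = 47.1% | 12.7% |

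The rows up to 5% fit the SAP's gap, which covers only lymphoma deaths with nothing recorded. The 10% and 15% rows would need a much larger loss, as could happen if Protocol 10.5 were applied literally and every early progressor without a post-dose assessment were dropped.

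**One data set (16 responders assumed), one-sided exact p against 40%.** 16/30 = 53.3%, p = 0.097. One dropped: 16/29 = 55.2%, p = 0.071. Two dropped: 16/28 = 57.1%, p = 0.0499. Three dropped: 16/27 = 59.3%, p = 0.034. One lost patient does not change the conclusion here at 5%; two or three would.

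**The case against.** The strongest reply is that the SAP governs, and the SAP already keeps the main group. Protocol 10 leaves the full description of the analyses to the SAP, SAP 10.2 uses the efficacy evaluable set, and SAP 7.3 includes clinical progression, which agrees with the futility definition. Protocol 10.2 asks for evaluable disease rather than a scan, and Protocol 10.5 says radiographic only for the baseline assessment, so SAP 7.3 can be read as a clarification. This largely stands. It reduces the problem under the SAP to deaths with nothing recorded, and makes the smaller figures the relevant ones. It does not supply a rule for those deaths, and SAP 11 still does not say that the protocol's wording has been changed.

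Three stronger readings are tempting, and the documents do not support them.

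- A reader might infer that the final ORR drops everyone who progresses before the first scan. SAP 7.3 keeps those with recorded clinical progression.
- A reader might infer that ORR will be reported on a per-protocol denominator that conflicts with the primary one. No visible text plans ORR on the per-protocol set; its visible use is for disease characteristics (SAP 10.1.6.1). Blacked-out text may say more, but that cannot be assumed.
- A reader might take the reference in SAP 7.3 to Protocol 10.2 as a false claim of support for the clinical progression clause. The reference belongs to the next sentence, on reporting by assigned treatment, and Protocol 10.2 does say that.

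The add-on in SAP 7.4 may also have a purpose. The same section excludes patients when data needed to interpret the primary efficacy endpoints were not collected, and the sentence may be there to protect cycle 1 deaths from that exclusion. Simply deleting it could remove failures from the per-protocol set. That stands and shapes the fix.

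**Conclusion.** The point holds in a limited form. SAP 7.3 has no place for a lymphoma death before the first scan without recorded clinical progression. SAP 7.4 restores such a death only in cycle 1 and only to the per-protocol set, which is then not a subset of its parent; from day 22 to the first scan these deaths are in neither set. Protocol 10.5 differs from the futility definition and SAP 7.3 on early progression, and SAP 11 does not record this.

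The direction is certain, because only non-responders are lost; this follows from ORR being the proportion with a best response of PR or CR. The size is probably small under the SAP: a rejection rate of 5.2% to 6.5% instead of 4.8% if 2% to 5% of patients are affected. Rates of 9.1% to 12.7% apply only if 10% to 15% are dropped. All of these rest on the assumed 30 patients, true ORR of 40%, one-sided 5% level and shares dropped; the documents do not give the number of such deaths. The correction should be made because it is cheap and settles the denominator of a primary endpoint.

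**What to change.** 1. **SAP 7.3.** After the mention of clinical progressive disease, add *or death from disease progression before the first post-baseline assessment*, and state that these patients count as non-responders in ORR.
2. **SAP 7.4.** Replace the add-on sentence with a statement that patients with clinical progression, or death from disease progression, before the first post-baseline assessment are not excluded from the per-protocol set for missing post-baseline tumor data. With the change to SAP 7.3, the set then nests and still keeps these patients.
3. **Protocol 10.5 and 10.2.** Align the wording with SAP 7.3, or record the difference in SAP 11 as a change from the protocol.

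The cost is wording, with no new data collection beyond the cause and date of death already planned. The downside for the sponsor is that ORR may come out slightly less favourable.
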